# **Ertu-GLS Randomized Clinical Trial Protocol**

## **1. Objectives**

The aim of this study is to investigate the beneficial effects of ertugliflozin, a novel sodium-glucose cotransporter 2 (SGLT2) inhibitor, on cardiac function by assessing global longitudinal strain (GLS) and other hemodynamic parameters through echocardiography in individuals with type 2 diabetes (T2D) and pre-heart failure (pre-HF)

## **2. Hypothesis**

We hypothesize that ertugliflozin will improve cardiac function in individuals with T2D and pre-heart failure.

## **3. Study design**

[figure not shown]
This randomized, double-blind, placebo-controlled, parallel-group trial aims to enroll 120 participants. Individuals with T2D who have been on pharmacological treatment for at least 12 weeks, without any dose adjustments prior to enrollment, will be eligible for screening. The screening period will last up to two weeks before randomization. To qualify for randomization, participants must meet an 80% compliance rate, based on pill count, and the investigator's discretion during the run-in phase. After randomization, participants will be blinded to their glycated hemoglobin (HbA1c) and fasting plasma glucose (FPG) results. To maintain blinding, urinary glucose excretion (UGE) results will also be masked from participants. Urine glucose, albumin, calcium, and creatinine will be measured separately during on-site visits.

## **4. Study participants**

### **4.1. Inclusion criteria**

- Individuals with T2D on stable oral antidiabetic medications, excluding SGLT2 inhibitors, for at least 12 weeks prior to enrollment, with no dose adjustments
- Estimated glomerular filtration rate (eGFR)  $\geq 45$  mL/min/1.73 m^2
- Pre-heart failure (pre-HF), or stage B heart failure (HF), identified based on structural or functional markers (Fig. 1) [1, 2]:
  - Structural abnormality defined as moderate left ventricular hypertrophy (LVH),

- indicated by a left ventricular mass index (LVMI)  $\geq 95$  g/m^2 in women or  $\geq 115$  g/m^2 in men
- Functional impairment defined as E/e'  $> 15$  and/or left ventricular global longitudinal strain (LVGLS)  $> -16\%$

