A recent study demonstrated a strong positive correlation between GLS and ejection fraction (EF), particularly in individuals with LV systolic impairment ( $r=0.95$ ;  $P<0.001$ ) [7]. In contrast, LV ejection had a relatively weaker correlation with LV twist and torsion. Another study also showed that semi-automated GLS analysis had a strong correlation with EF, regardless of whether it was performed by experienced readers ( $r=0.98$ ) or less experienced readers ( $r=0.91$ ) (Fig. 2) [8]. The semi-automated GLS measurements exhibited less bias between experienced and less experienced readers ( $-1.0 \pm 13\%$ ) compared to EF measurements ( $-3.5 \pm 6.7\%$ ). Furthermore, repeated GLS measurements showed higher intra-class correlation ( $ICC=0.98$ ) compared to EF ( $ICC=0.89$ ). GLS analysis also takes less time, approximately one minute per patient, whereas biplane EF measurements take twice as long. Thus, semi-automated GLS measurements are faster, less dependent on experience, and more reproducible than conventional EF measurements.

In a recent study involving individuals with advanced chronic kidney disease, GLS was found to be a significant predictor of all-cause mortality [hazard ratio (HR), 1.09; 95% confidence interval (CI), 1.02–1.16;  $P<0.05$ ] and cardiovascular (CV) mortality (HR, 1.16; 95% CI, 1.04–1.30;  $P<0.05$ ), even after adjusting for clinical factors such as LVMI and EF [9]. Notably, GLS had greater predictive power for both all-cause and CV mortality compared to EF. Impaired GLS ( $>-16\%$ ) was associated with a 5.6-fold increased risk of CV mortality, even in individuals with preserved EF. Collectively, these findings suggest that GLS is a valuable measure for reflecting myocardial function.

**Fig. 2. Left ventricular global longitudinal strain and volumes.** After the endocardial boundaries are defined by the user, the software generates global longitudinal strain curves throughout the cardiac cycle. These curves quantify myocardial deformation, represented as strain values, across the 4-chamber, 3-chamber, and 2-chamber views [8].

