## **6. Study outcomes**

### **6.1. Primary outcome**

- Changes in LVGLS after ertugliflozin treatment in individuals with T2D and pre-HF compared to placebo.

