## 7. Treatment

### 7.1. Intervention and control

After randomization, patients will undergo a 24-week double-blind treatment period. A total of 102 patients aged 20 years or older will be randomly assigned in a 1:1 ratio to one of the following two groups:

- Ertugliflozin 5 mg once daily
- Placebo (identical in appearance to ertugliflozin) once daily

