## 8. Sample size calculation

The primary endpoint of this study is the change in LVGLS from baseline to week 24. The hypothesis is that the ertugliflozin group will demonstrate superiority over the placebo group.

- Null hypothesis ( $H_0$ ):  $P_1 = P_2 \geq \delta$
- Alternative hypothesis ( $H_1$ ):  $P_1 - P_2 < \delta$

The following equation will be used for sample size estimation:

When  $r = 1$ ,

1. Type I error ( $\alpha$ ) = 5% (two-sided, default)
2. Power = 1 – Type II error ( $\beta$ ) = 80% (default)
3. Allocation ( $r$ ) = 1 (default)
4. Mean in the ertugliflozin group ( $\mu_1$ )
5. Mean in the placebo group ( $\mu_2$ )

6. Standard deviation (SD) in the ertugliflozin group ( $SD_1$ )
7. SD in the placebo group ( $SD_2$ )
8. Dropout rate ( $d$ ) = 10% (default)

Since no prior interventional studies have evaluated the effect of ertugliflozin on GLS, we referenced studies measuring LV volume. An increase in LV volume has been used as a marker for assessing the impact of drug therapy on heart failure survival [13]. It has been suggested that a 10 mL change in LV volume is clinically significant [14]. This change corresponds to a 15% change in EF in individuals with pre-HF, whose EF typically ranges from 30% to 50%. In heart failure populations, the SD for the mean difference in LV volume has been reported to be 7.5 [15]. For comparison, the EMPA-REG OUTCOME trial showed that empagliflozin reduced heart failure hospitalization by 35% [16], and the CANVAS program found that canagliflozin reduced heart failure hospitalization by 33% [17]. Based on these results, we assumed a 15% baseline GLS in both groups and a 13.2% decrease in GLS in the ertugliflozin group after treatment, with no change in the placebo group. We assumed a standard deviation of 3.5 for both groups, adopting a conservative approach. Considering an 18% dropout rate, the minimum required sample size is 100 participants (60 per group with a 1:1 randomization). Additionally, a recent study demonstrated that improvements in glycemic control (HbA1c reduction from  $10.3 \pm 2.4\%$  to  $8.3 \pm 2.0\%$ ) over a 12-month period led to a 21% improvement in GLS and a 24% improvement in cardiac function, as estimated by septal e' [18].

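### Patients with non-impaired LVGLS can enter on LVMI or E/e' alone, and the LVGLS primary comparison neither stratifies by nor adjusts for baseline LVGLS

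*Combined protocol and SAP*

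**What the plan says.** Section 4.1 requires pre-heart failure "identified based on structural or functional markers". The structural route is "Structural abnormality defined as moderate left ventricular hypertrophy (LVH"), set by an LVMI cut-off of 95 g/m² in women and 115 g/m² in men. The functional route is E/e' above 15 and/or LVGLS above -16%. Neither Section 4.1 nor Section 4.2 sets an LVGLS or ejection-fraction limit that every patient must meet.

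Section 5.1 labels LVGLS above -16% as impaired and reports that it "was associated with a 5.6-fold increased risk of CV mortality, even in individuals with preserved EF".

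Section 6.1 defines the primary outcome for the whole population: "Changes in LVGLS after ertugliflozin treatment in individuals with T2D and pre-HF compared to placebo". Section 8 makes this the change from baseline to week 24.

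For the sample size, Section 8 states "we assumed a 15% baseline GLS in both groups and a 13.2% decrease in GLS in the ertugliflozin group after treatment", with no change on placebo. The calculation enters this as group means of 17 and 15 (absolute values) with SD 3.5. The supporting argument refers to pre-heart-failure patients "whose EF typically ranges from 30% to 50"%.

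Section 7.1 says only that patients "will be randomly assigned in a 1:1 ratio to one of the following two groups". No stratification factor, adjustment for baseline LVGLS or estimate by baseline LVGLS is described anywhere.

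**The concern.** The plan's own cut-off splits the eligible population on the primary endpoint variable, yet the design makes no use of that split. A patient whose strain is already normal may have less to gain on LVGLS. If so, each such patient pulls the pooled difference towards zero, and a sample size with no reserve loses power. After a null result it would be unclear whether the drug fails to improve impaired strain or whether a benefit in impaired patients was averaged away. A subgroup analysis chosen at that stage would be post hoc.

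There is also a smaller issue of precision. Baseline LVGLS can be expected to predict the change in LVGLS, and chance differences between arms in the share of impaired patients add avoidable noise in a trial of this size.

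**Working it through.** **1. Does the entry rule admit non-impaired strain?** Take a woman with LVMI 96 g/m², E/e' 10 and LVGLS -20%. She meets the structural criterion (96 ≥ 95), and nothing in Section 4.2 excludes her on strain or ejection fraction. She is eligible and, by the -16% boundary, not impaired.

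**2. The plan's sample size.** Inputs from Section 8: difference 17 - 15 = 2, SD 3.5, two-sided alpha 0.05, power 80%.

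n per arm = 2 × [3.5 × (1.960 + 0.842) / 2]² = 48.07, so 49 per arm and 98 in total. The plan prints 46 and 92, which these inputs do not give. With 18% dropout, 98 / 0.82 = 119.5, so 120, which is the total in Section 3. The 102 in Sections 7.1 and 8 corresponds to 92 with 10% dropout (92 × 1.10 = 101.2, rounded up). That conflict is a separate matter; here it only decides which n to use. I take 49 evaluable per arm for the pooled comparison and 51 per arm (102 / 2) where the Section 7.1 total applies.

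**3. Sensitivity of the pooled comparison.** Let f be the share with impaired LVGLS and λ the effect in the others relative to 2 points. Both are assumptions. The average difference is d = 2 × [f + (1 - f) × λ]. Power is from the two-sided t-test with SD 3.5 and 49 per arm.

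| Share non-impaired (1 - f) | d, λ = 0.5 | Power | d, λ = 0 | Power |
|---|---|---|---|---|
| 0% | 2.0 | 80.0% | 2.0 | 80.0% |
| 10% | 1.9 | 75.8% | 1.8 | 71.2% |
| 20% | 1.8 | 71.2% | 1.6 | 61.0% |
| 30% | 1.7 | 66.3% | 1.4 | 50.0% |

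With λ = 1, power is 80.0% in every row. The table takes 2 points as the effect in impaired patients, which the plan does not say.

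**4. An illustrative mix, used only to size the fix.** If SD 3.5 were the between-patient SD of baseline LVGLS and the distribution were normal with mean 15, the impaired share would be Φ((16 - 15) / 3.5) = Φ(0.286) = 0.612, leaving about 39% non-impaired (37% at SD 3.0, 34% at SD 2.5). The documents do not say that the SD describes baseline, and a plain normal curve ignores the selection made by the entry rule.

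**5. What stratifying and adjusting would gain.** At 51 per arm, the SD of the chance difference between arms in the impaired share is √(0.612 × 0.388 × 2 / 51) = 0.096, about 10 percentage points. With equal variances at both visits and correlation ρ between them, baseline explains (1 - ρ) / 2 of the variance of the change: 25% at ρ = 0.5 and 10% at ρ = 0.8 (assumed range). Splitting a normal baseline at 0.286 SD above its mean keeps φ(0.286)² / (0.612 × 0.388) = 0.383² / 0.237 = 0.62 of that. The stratum factor therefore removes 0.62 × 25% ≈ 15% down to 0.62 × 10% ≈ 6% of the variance; continuous baseline LVGLS removes the full 25% to 10%.

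**6. What the stratum estimate can show.** The impaired stratum would have 51 × 0.612 ≈ 31 per arm and the other stratum about 20.

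- Power for 2 points in the impaired stratum: about 60%. After 18% dropout (31.2 × 0.82 = 25.6 per arm): about 52%.
- Interaction: SE = 3.5 × √(2/31 + 2/20) = 1.42. Power is about 29% if the non-impaired gain nothing (difference 2) and about 11% if they gain half (difference 1), before dropout.

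**The case against.** The strongest reply is that entry rule and endpoint agree with the stated aim. Sections 1 and 2 concern cardiac function in type 2 diabetes with pre-heart failure, not impaired strain, and Section 6.1 takes the same population. Randomisation gives a valid average effect in it. This stands. A reader might infer that a null result could not be interpreted at all; the documents do not support that. A null would speak to the average effect in pre-heart failure as defined, and would leave only the effect in impaired patients open.

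A second reply is that Section 8 gives group means, and a mean of 15 is compatible with some patients beyond 16. The 2 points may already be the average over the mix. This also stands. A reader might combine the 39% from step 4 with zero effect in those patients and conclude that true power at 51 per arm is about 42%. That takes the mix from the plan's mean and SD and then reassigns the plan's average effect to impaired patients only, a step with no support in the documents.

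Third, chance imbalance is already reflected in the standard error of a randomised comparison. True; the gain from stratifying and adjusting is precision, not removal of bias. Section 7.1 is also silent on the randomisation method, so the gap is that no stratification is described, not that an unstratified scheme is specified.

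Finally, the stratum estimate is itself underpowered, so it cannot settle a null. That is correct, and it limits the estimate to a supportive role.

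**Conclusion.** The point holds as a moderate design weakness. It is certain from the text that patients with non-impaired LVGLS can be randomised, that they are pooled in the primary comparison, and that no stratification or adjustment by baseline LVGLS is described. Dilution is conditional: it needs a smaller effect at normal strain, and the documents give neither an effect by baseline LVGLS nor an expected mix. Under the ranges in step 3, 10% to 30% non-impaired patients would bring power from 80% to between 76% and 50%; under a uniform effect, or if 2 points is already the average over the mix, nothing is lost against the plan. The gain in precision does not depend on the dilution assumption: about 6% to 15% less variance of the change score from the stratum factor, for correlations of 0.8 to 0.5 and the illustrative mix.

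**What to change.** - **Section 7.1:** stratify the 1:1 randomisation by screening LVGLS (above -16% versus -16% or better).
- **Primary analysis:** include that stratum, or baseline LVGLS, in the model for LVGLS change at week 24. The pooled comparison remains primary.
- **Section 6:** prespecify the ertugliflozin-placebo difference in LVGLS change within the stratum above -16%, with the treatment-by-stratum interaction, labelled supportive and not confirmatory.

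The cost is one two-level randomisation factor and one additional analysis, with no extra patients. Strain must be read before randomisation for every patient, including those entering on LVMI or E/e'; Section 5.1 already plans the three apical views. The limits should be stated alongside: about 60% power for 2 points in the impaired stratum (about 52% after 18% dropout) and about 11% to 29% for the interaction, on the illustrative mix. Restricting entry to impaired LVGLS would change the target population and slow recruitment; it is a trade-off for the sponsor and is not part of this fix.

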**Fig. 1. Stages in the development of HF and recommended therapy by stage [1].**

## 4.2. Exclusion criteria

- Individuals with type 1 diabetes
- Age  $<20$  years at the time of screening
- HbA1c  $<7.0\%$  or  $>9.5\%$  at screening
- FPG  $>15$  mmol/L (270 mg/dL) at screening (Visit 1), confirmed by a repeat test prior to randomization
- Use of a glucagon-like peptide-1 (GLP-1) receptor agonist within 12 weeks prior to the screening visit

- Women of childbearing potential without an effective contraceptive method
- History of gastric surgery, including gastric banding, within 3 years before the screening visit
- History of diabetic ketoacidosis or nonketotic hyperosmolar coma prior to screening.
- Mean systolic blood pressure (BP)  $>180$  mmHg or diastolic BP  $>95$  mmHg after three separate measurements
- History or current symptoms of HF
- Severe anemia, or severe respiratory, hepatic, neurological, or psychiatric disorders; active malignant neoplasms; or any major systemic disease or short life expectancy that would hinder protocol implementation or interpretation of study results
- Aspartate aminotransferase (AST) or alanine aminotransferase (ALT) levels more than three times the upper limit of normal (ULN)
- Total bilirubin  $>1.5$  times the ULN (except for Gilbert syndrome)
- Use of systemic glucocorticoids (excluding topical, ophthalmic, or inhaled forms) for more than 10 consecutive days within 90 days prior to screening
- Participation in another investigational drug trial or use of prohibited therapies within 3 months prior to screening

## 5. Major investigation

### 5.1. GLS by transcardiac echocardiography

The standard commercially available cardiac ultrasound machines (Vivid 7 and Vivid E9, General Electric Medical Systems, Milwaukee, WI, USA) will be used to perform resting echocardiograms. Images will be saved in raw data format for offline analysis to assess left ventricular (LV) wall thickness, valvular morphology, chamber volumes, and global 2D strain. LV mass will be measured using standard criteria and normalized to body surface area to obtain the LVMI [3]. LVH will be determined following the recommendations of the American Society of Echocardiography and the European Association of Echocardiography [4]. The modified Simpson's biplane method will be used to measure the LV ejection fraction (LVEF).

[figure not shown]
Pulsed wave Doppler recordings of LV inflow will be acquired from the apical four-chamber view with the sample volume placed between the tips of the mitral leaflets. Peak early (E) and late diastolic flow velocities (A), the E/A ratio, and deceleration time of early diastolic flow will be measured. Pulsed wave tissue Doppler will be performed to assess peak early

diastolic mitral annular velocity ( $e'$ ). The ratio of mitral inflow early diastolic velocity to the average  $e'$  velocity obtained from the septal and lateral sides of the mitral annulus ( $E/e'$ ) will be calculated to estimate LV filling pressure, with a value  $>15$  indicating elevated LV filling pressure [5].

For global 2D strain analysis, digital loops will be acquired from standard apical four-chamber, three-chamber, and two-chamber views. The LV endocardial border will be traced at the end-systolic frame. The strain curve will be derived from the gray-scale images using dedicated software (EchoPAC, GE, Vingmed, Norway). Peak strain will be defined as the peak negative value on the strain curve during the cardiac cycle. Peak GLS will be calculated for the entire U-shaped LV myocardium as:  $LVGLS (\%) = [(L \text{ end-systole} - L \text{ end-diastole}) / L \text{ end-diastole}] \times 100$  [6], where “ $L$ ” represents the length of the entire LV myocardium, considered as one continuous segment. GLS will be averaged across the apical 4-, 3-, and 2-chamber views.

A recent study demonstrated a strong positive correlation between GLS and ejection fraction (EF), particularly in individuals with LV systolic impairment ( $r=0.95$ ;  $P<0.001$ ) [7]. In contrast, LV ejection had a relatively weaker correlation with LV twist and torsion. Another study also showed that semi-automated GLS analysis had a strong correlation with EF, regardless of whether it was performed by experienced readers ( $r=0.98$ ) or less experienced readers ( $r=0.91$ ) (Fig. 2) [8]. The semi-automated GLS measurements exhibited less bias between experienced and less experienced readers ( $-1.0 \pm 13\%$ ) compared to EF measurements ( $-3.5 \pm 6.7\%$ ). Furthermore, repeated GLS measurements showed higher intra-class correlation ( $ICC=0.98$ ) compared to EF ( $ICC=0.89$ ). GLS analysis also takes less time, approximately one minute per patient, whereas biplane EF measurements take twice as long. Thus, semi-automated GLS measurements are faster, less dependent on experience, and more reproducible than conventional EF measurements.

In a recent study involving individuals with advanced chronic kidney disease, GLS was found to be a significant predictor of all-cause mortality [hazard ratio (HR), 1.09; 95% confidence interval (CI), 1.02–1.16;  $P<0.05$ ] and cardiovascular (CV) mortality (HR, 1.16; 95% CI, 1.04–1.30;  $P<0.05$ ), even after adjusting for clinical factors such as LVMI and EF [9]. Notably, GLS had greater predictive power for both all-cause and CV mortality compared to EF. Impaired GLS ( $>-16\%$ ) was associated with a 5.6-fold increased risk of CV mortality, even in individuals with preserved EF. Collectively, these findings suggest that GLS is a valuable measure for reflecting myocardial function.

**Fig. 2. Left ventricular global longitudinal strain and volumes.** After the endocardial boundaries are defined by the user, the software generates global longitudinal strain curves throughout the cardiac cycle. These curves quantify myocardial deformation, represented as strain values, across the 4-chamber, 3-chamber, and 2-chamber views [8].

## 5.2. Body composition analysis using bioelectrical impedance analysis

[figure not shown]
Whole body fat mass and fat percentage are measured using bioelectrical impedance analysis (BIA), a widely used method for estimating body composition by analyzing the impedance generated when a current flows through the body. This noninvasive, simple, and cost-effective technique has evolved from earlier single-frequency systems to the more accurate multifrequency systems used today. To date, body composition data—including whole-body fat mass, fat percentage, and muscle mass—obtained via BIA has been used in over 2,000 studies, including our own, according to a PubMed search conducted on June 15, 2015 [10, 11].

Participants are instructed to avoid smoking, alcohol consumption, and strenuous exercise for 48 hours prior to measurement. After standing on the device platform, age and gender information is entered into the machine. The participant's posture is confirmed, with arms slightly apart from the body and feet placed correctly on the platform, before a supervisor initiates the assessment. The hands are positioned at a 45-degree angle away from the body. The BIA device, such as the X-scan model, uses multiple frequencies (1, 5, 50, 250, 500 kHz, and 1 MHz) to assess intracellular and extracellular fluid levels, as well as total body water content.

Abdominal visceral fat area (VFA) is also estimated using three multifrequency BIA devices (InBody 720; InBody Co., Seoul, Korea), with participants measured in a fasting state on the same day as their blood tests [10].

### 5.3. Biomarkers

Recent studies have identified a new regulatory axis within the renin-angiotensin system (RAS) (Fig. 3). In this axis, angiotensin (1-7) is ultimately produced from either angiotensin I or II through the catalytic activity of angiotensin-converting enzyme 2 (ACE2).

